[name], Research Assistant Professor of Psychiatry and Biostatistics and Director of the Division of Quantitative Methods in the Department of Psychiatry UCCOM, has extensive expertise in the area of psychiatry and biostatistics. [name] will oversee all aspects related to database design and data management. He will lead the statistical analyses and complete exploratory post-hoc analyses. He will also assist in preparing manuscripts of the research findings.

E. Experimental Design and Methods:

Figure 1. Schedule of assessments for the 14-week trial

ASSESSMENT	SCREENING	BASELINE	WEEKS 1-11	WEEK 12 (TERMINATION)	WEEK 14 (FOLLOW-UP)
WASH-U KSADS	X	X			
Young Mania Rating Scale (YMRS)	X	X	X	X	X
Children's Depression Rating Scale-Revised (CDRS-R)	X	X	X	X	X
ADHD Rating Scale (ADHD Rating Scale-IV)	X	X	X	X	X
Clinical Global Impression-Severity (CGI-S)	X	X	X	X	X
Clinical Global Impression-Improvement (CGI-I)			X	X	X
Timeline Follow-Back	X	X	X	X	X
Child Behavior Checklist (CBCL)		X	X (Wk 4 & 8)	X	X
Teacher's Report Form (TRF)		X		X	
Children's Global Assessment Scale (CGAS)	X	X	X (Wk 4 & 8)	X	X
The Omega-3 Dietary Intake Questionnaire		X	X	X	
Columbia Suicide Severity Rating Scale (C-SSRS)	X	X	X	X	X
LIFE psychosocial functioning scales		X	X (Wk 4 & 8)	X	
Prior medical & treatment history, physical exam	X			X (physical exam)	
Vital signs	X	X	X	X	X
Urine toxicology screen & pregnancy test	X	X		X	
Serum laboratory tests (renal profile, complete blood count, liver & thyroid function tests, fasting lipid profile & glucose, and platelet function assay)	X			X	
Red blood cell omega-3 fatty acid levels	X			X	
Adverse events & adherence assessments	X	X	X	X	X
¹ H-MRS scan		X		X	
Total duration of appointment	2 hours	3 hours	1 hour	3 hours	1-2 hours

Figure 2. Study Design

DBPC=Double-blind placebo-controlled; SOC=Standard of Care Treatment

a. Methods and Procedures:

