A randomization schedule stratified by presence vs. absence of ADHD, presence vs. absence of concomitant stimulant treatment (within the ADHD group), and pre-pubescent vs. post pubescent (as determined by the Tanner Questionnaire with scores of 1-2 representing pre-pubescent and scores of 3-5 indicating post-pubescent) will be developed by the on-site biostatistician and will be used to assign omega-3 fatty acids (N=30) or placebo (N=30) treatment in a double-blind manner. We will stratify treatment assignment by some of the independently transmitted variables that contribute to the heterogeneity of at-risk adolescents (i.e. ADHD and concomitant use of stimulants) so that we will be able to assess the effects of these clinical factors on the neurophysiological and omega-3 fatty acid RBC level changes associated with supplementation of omega-3 fatty acids (vs. placebo) and examine potential neurophysiological markers of treatment response within clinically defined subgroups. We selected these variables for stratification because they may each affect outcome and treatment response.

Twelve-week Study Phase: During the 12-week DBPC phase subjects will participate in weekly research visits to assess symptom response and adverse side effects. Following the randomization visit, all visits will be scheduled weekly (or ≤ 10 days apart). The research visits will take approximately 1 hour; at these visits an experienced clinician will evaluate the patients for adverse effects and clinical response. Efficacy assessments will be obtained by a rater who is blind to side effects.

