Image acquisition and fMRI: fMRI evaluations will be obtained on subjects at the baseline visit and at 12 weeks. All subjects will be scanned at the University of Cincinnati College of Medicine's Center for Imaging Research (CIR) using a 4.0 Tesla Varian Unity INOVA Whole Body MRI/MRS system (Varian Inc., Palo Alto, CA). The INOVA system is controlled by a SUN workstation running Varian's VNMR-JTM and SPIN-CADTM image processing and pulse-sequence development software under a Unix-based operating system. Data are stored on a networked hard drive (for off-line analysis) and additionally backed up by burning onto CDs or DVDs.

During the scan sessions, subjects recline in a supine position on the scanner bed. Nonferromagnetic goggles are positioned to provide clear visualization of the stimuli and a radio-frequency (RF) coil is placed over the subject's head. Padding is inserted around the subject's head to minimize movement. Headphones are provided to block background noise and so that investigators can communicate with the subjects during scan acquisition. A microphone in the scanner permits subjects to communicate with the MRI technician in case of concern or discomfort.

Following a three-plane gradient echo scan for alignment and brain localization, a shim procedure is performed to generate a homogeneous magnetic field. To provide anatomical localization for activation maps, a high-resolution, T1-weighted, 3-D brain scan is obtained using a modified driven equilibrium Fourier transform (MDEFT) sequence ($T_{MD}=1.1$ s, $TR=13$ ms, $TE=6$ ms, $FOV=25.6 \times 19.2 \times 19.2$ cm, matrix $256 \times 192 \times 96$ pixels, flip angle=20 degrees). A midsagittal localizer scan is obtained to place 40 contiguous 4 mm axial slices that extend from the inferior cerebellum to encompass the entire brain. Subjects then complete an fMRI session in which scans

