Patients: This is a 12-week double-blind randomized investigation of omega-3 fatty acid (N=30) vs. placebo (N=30) for the treatment of major depressive disorder and depressive disorder NOS in adolescents (N_{Total}=60). Patient selection will be done by research staff in consultation with and with permission from the PI. Inclusion/Exclusion criteria are found below (see F., 3.).

Healthy Controls: Although we will not recruit healthy subjects for the proposed study, they are recruited (n=40) already for BITREC Project 3 and undergo an initial ¹H-MRS scan. Therefore, we will be able to interpret the direction of neurobiological changes in at-risk adolescents (i.e., whether patient values are changing toward or away from those of healthy adolescents).

2. Estimated sample size: We propose to randomize 30 subjects per treatment group, for a total of 60 subjects at the University of Cincinnati. As this is an investigator-initiated protocol, there are no other sites associated with this submission.

Based on our prior studies, we estimate that approximately 25% of patients will either discontinue study participation prior to completing study procedures or will not have usable MRS data. For the power calculations described, we considered medium to large effect sizes of $d > 0.6-0.8$ to be clinically relevant.⁷⁹

3. Description of Inclusion/Exclusion Criteria

Inclusion Criterion:

- Ages 9 -21 years old.
- At least one biological parent with bipolar I disorder.
- Meets DSM-IV-TR⁸⁰ criteria for major depressive disorder (MDD) or Depressive Disorder NOS at screening as determined by the Washington University at St. Louis Kiddie Schedule for Affective Disorders and Schizophrenia, WASH-U-KSADS;⁸¹
- Childhood Depression Rating Scale-Revised Version^{40,41} (CDRS-R) scores ≥ 28 at screening and baseline.
- Fluent in English.
- Provision of written informed consent/assent as previously described.
- Agrees to use one of the following method of birth control: complete abstinence from sexual intercourse, barrier (diaphragm or condom), or oral/injectable contraceptive.

Exclusion Criterion:

- Contraindication to an MRI scan (e.g., metal clips, braces or claustrophobia).
- Mood symptoms resulting from acute medical illness or acute intoxication or withdrawal from drugs or alcohol as determined by careful medical evaluation or rapid symptom resolution.
- Psychotic symptoms (i.e., hallucinations or delusions).
- Any lifetime history of a manic or hypomanic episode.

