Although a number of prior studies indicate omega-3 fatty acid supplementation is beneficial to pregnancy and a developing fetus, many studies have been inconclusive. Thus, there may be unknown teratogenic effects on a fetus exposed to high levels of omega-3. In order to decrease the risk of harm to females and their fetus if pregnant, pregnancy at any point while enrolled is

exclusionary for this protocol. Urine pregnancy screens at time points throughout study participation are performed to verify a subject's verbal declaration of not being pregnant, or verbal declaration to the contrary. All potential female participants are informed, verbally and through the informed consent document, that pregnancy is exclusionary at all times and that getting pregnant may expose that individual and her fetus to unknown risks. Participants will be reminded of pregnancy exclusion and risks during study visits.

Although there is no known risk to subjects or their fetus if receiving an MRI scan, exposing subjects or their fetus to the high magnetic fields generated by an MRI machine may involve unknown risks. Thus, subjects will not be pregnant at any point in this study.

Any subject who becomes pregnant during participation in a clinical study for which pregnancy is a standard exclusion criterion must be promptly withdrawn from the study. Long-term follow-up information regarding the outcome of the pregnancy and any postnatal sequelae in the infant will be required. We will be monitoring all female subjects for pregnancy each month. Subjects receiving an MRI will receive a urine pregnancy before receiving a scan.

The effects of the drugs on the male reproduction are not entirely known. Therefore, male subjects should not cause a pregnancy. If a male subject causes a pregnancy during this study, long-term follow-up information regarding the outcome of the pregnancy and any postnatal sequelae in the infant may be required.

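### Monthly pregnancy monitoring is promised, but the schedule has no pregnancy test between baseline and week 12

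*Combined protocol and SAP*

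**What the plan says.** Section G.3.d makes four statements about pregnancy during the trial:

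- On frequency: "We will be monitoring all female subjects for pregnancy each month".
- On verification: "Urine pregnancy screens at time points throughout study participation are performed to verify" what a subject declares about being pregnant or not.
- On imaging: "Subjects receiving an MRI will receive a urine pregnancy before receiving a scan".
- On consequence: a subject who becomes pregnant "must be promptly withdrawn from the study". The reason given is that effects on a fetus at high omega-3 levels are unknown.

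The schedule of assessments (Figure 1, Section E) has one row for this, "Urine toxicology screen & pregnancy test". It is marked at screening, baseline and week 12 (termination). The weeks 1-11 and week 14 cells are blank.

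Under Twelve-week Study Phase in Section E.a, "all visits will be scheduled weekly" after randomization, with up to 10 days allowed between them. Scans occur twice: "fMRI evaluations will be obtained on subjects at the baseline visit and at 12 weeks". Among the inclusion criteria in Section F.3 is that the subject "Agrees to use one of the following method of birth control", with abstinence as one option.

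**The concern.** G.3.d commits to a monthly frequency, and Figure 1 has no entry that delivers it. Prompt withdrawal depends on detection, and G.3.d treats self-report as something that a urine screen should confirm. Staff who work from Figure 1 would have no scheduled confirmation between the start and the end of supplementation.

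The stake is safety: supplement exposure in an undetected pregnancy, in a population aged 9 to 21. There is also a compliance issue. An ethics board that reads G.3.d would expect monthly monitoring that the schedule does not contain. Neither the efficacy analysis nor the error rates are involved.

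**Working it through.** The plan gives no numerical figure to reproduce here. The check sets the texts side by side and counts.

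**1. Is the blank cell real?** The row keeps its column order, and its three marks fall on the screening visit and the two scan visits. In the same table, the CBCL, CGAS and LIFE rows are marked for weeks 4 and 8 within the weeks 1-11 column. The authors therefore had a notation for four-weekly assessments and did not use it for the pregnancy test.

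**2. Do the pre-scan tests fill the gap?** No. Scans are at baseline and week 12, and Figure 1 already shows a test at both. The pre-scan sentence adds no test between them.

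**3. Size of the gap.**

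- Visits in weeks 1-11: 11. Pregnancy tests scheduled at them: 0.
- Nominal interval from baseline to week 12: 12 × 7 = 84 days. It is shorter for a subject who leaves early and is tested at termination.
- The 84 days is not a maximum. If all 12 intervals ran to the permitted 10 days, it would be 12 × 10 = 120 days.

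**4. Missing tests under each reading of monthly monitoring.**

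| Reading | Expected after baseline | Scheduled | Missing |
|---|---|---|---|
| Urine test | 3 (weeks 4, 8, 12) | 1 (week 12) | 2 |
| Self-report and reminders | no interim test | 1 (week 12) | 0 |

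Under the second reading no test is missing, but nothing verifies self-report between baseline and week 12.

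**5. Number of tests added by the correction.** Inputs: 60 subjects (F.2), equal numbers of each sex expected (F.4), and about 25% lost to dropout or unusable MRS data (F.2).

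- No early dropout: 2 × (60 × 0.5) = 60 tests.
- The whole 25% lost before week 4: 2 × (60 × 0.5 × 0.75) = 45 tests. On these inputs this is a lower bound, because the 25% also covers unusable scans in subjects who stay.

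With tests at weeks 4 and 8, the longest nominal gap between scheduled tests falls from 12 weeks to 4 × 7 = 28 days.

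**The case against.** The strongest reply is that monitoring is not testing. The monthly sentence names no test, and the sentence on urine screens gives no frequency. Tests at screening, baseline and week 12 could be said to satisfy it, and the one sentence that ties a urine test to an occasion, the scan, agrees with Figure 1. On that view the protocol lacks only a description of the monthly method. The wording may also be carried over from another protocol: Section G.3.d mentions a week 16 scan and cannabis-using subjects, neither of which fits this trial. Correcting the sentence might then be the right repair.

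Part of this stands. The method is not stated, so the count of missing tests is 2 or 0 depending on the reading. But G.3.d presents the monthly commitment separately from the pre-scan test, and Figure 1 shows nothing that carries it out under either reading. Tests only before dosing and at its end also fit poorly with screens spread across participation.

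Three further points:

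- **Young subjects.** Enrollment starts at age 9, and pre-pubescent status is a stratification factor, so some added tests would serve little purpose. However, G.3.d speaks of all female subjects, and the existing tests carry no pubertal limit.
- **Staff are bound by the whole protocol.** This is true, and nothing gives Figure 1 precedence. But G.3.d names no visits for monthly monitoring, so staff have no schedule to follow for it.
- **Consent forms.** They were not available for review and may describe testing. They would not remove the mismatch between the two texts.

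**Conclusion.** The concern holds. The protocol promises monthly pregnancy monitoring and verification by urine screen, yet it schedules no pregnancy test at any of the 11 visits between baseline and week 12, a nominal 84 days of dosing. Two tests are missing if monthly monitoring means urine testing. None is missing if it means self-report, but that reading leaves self-report unverified throughout the interval.

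The consequence is modest. Contraception or abstinence is required, subjects are reminded at visits, a clinician sees them weekly, and MRI exposure is covered by the pre-scan tests. What remains is unverified supplement exposure and later detection than prompt withdrawal requires. The correction should be made because it delivers the protocol's own commitment at very small cost. Confidence is medium, since the intended method of monthly monitoring has to be inferred.

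**What to change.** In Figure 1, separate the pregnancy test from the toxicology screen so that no extra toxicology tests follow. Mark the new pregnancy row at weeks 4 and 8, as is done for the CBCL, CGAS and LIFE, and keep the existing marks. In G.3.d, state that monthly monitoring is by urine test.

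If the sponsor does not intend interim tests, G.3.d should instead state the method and frequency to be used. That would align the texts but leave the interval between baseline and week 12 on self-report, so it is the weaker option.

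The cost is one table row and one sentence, plus at most two urine tests per female subject at visits that already take place: about 60 tests with no dropout, or about 45 if the full 25% loss came before week 4.
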